8.4. Vital Signs and Physical/Neurological Examination Findings

Descriptive statistics (N, mean, SD, median and range) for absolute values and changes from baseline will be presented at each scheduled time point and endpoint by treatment group for height, body weight and BMI. Similar summary tables will be presented for systolic blood

pressure (mmHg), diastolic blood pressure (mmHg), pulse rate (beats per minute) and temperature (°C).

Mean-SE plots over time will be presented for vital sign values by treatment group, and a subject data listing will be provided. In addition, scatter plots of post-baseline versus baseline values will be presented by treatment group.

Abnormal values are defined in [Table 6](#), and will be summarized using frequency distribution tables over time by treatment group. A listing of subjects meeting any of the abnormality criteria will be provided.

Table 6: Vital Signs Abnormality Ranges (Supine and Standing)

	Low	Normal	High
SBP (mmHg)	<90	90-140	>140
DBP (mmHg)	<50	50-90	>90
Pulse (bpm)	<45	45-90	>90
Temperature (C)	<35.5	35.5-37.5	>37.5

The incidence of subjects who have a treatment-emergent abnormality (as defined in [Table 7](#) below) at each scheduled time point and endpoint and at any time during the double-blind treatment phase will be presented by treatment group. Shift from baseline tables at each scheduled time point and endpoint will be generated for the vital signs values using the classes (below, within, and above normal ranges) for each treatment group.

Table 7: Treatment-Emergent Abnormality Categories for Vital Signs

Vital Parameter	Post-baseline value outside of normal limit if:	
	Abnormally low	Abnormally high
Pulse (bpm)	A decrease from baseline of ≥ 15 to a value < 45	An increase from baseline of ≥ 15 to a value > 90
Systolic BP (mmHg)	A decrease from baseline of ≥ 20 to a value < 90	An increase from baseline of ≥ 20 to a value > 140
Diastolic BP (mmHg)	A decrease from baseline of ≥ 15 to a value < 50	An increase from baseline of ≥ 15 to a value > 90

BP = blood pressure

A listing of subjects meeting any of the abnormality criteria will also be provided.

The orthostatic hypotension measurements will be calculated as the standing measurement minus the supine measurement. Orthostatic hypotension is defined as a decrease in systolic (>20 mmHg), or diastolic (>10 mmHg) blood pressure after standing for at least 2 minutes with an increase in pulse rate of >15 beats per minute ([Table 8](#)).

Table 8: Abnormal limits for orthostatic parameters

Vital Signs Parameter	Outside of normal limit if difference (Standing minus supine)
(1) Pulse (bpm)	> 15 bpm
(2a) Systolic blood pressure (mmHg) (SBP)	< - 20 mmHg
(2b) Diastolic blood pressure (mmHg) (DBP)	< -10 mmHg

Orthostatic hypotension requires that conditions (1) and [(2a) or (2b)] are met.

For subjects who are unable to stand and have the vital signs measured in a sitting or supine position instead of the standing position, the difference between standing and supine value will remain missing.

Frequency table of the occurrence of orthostatic hypotension at each scheduled time point and endpoint and at any time during the double-blind treatment phase will be presented by treatment group. Listings will be provided for subjects who have orthostatic hypertension.

Physical examination abnormalities and neurological examination results will be listed.

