#### Footnotes:

- a. Visits should be conducted within +/-3 days of the scheduled day.
- b. If a subject discontinues treatment before the end of the double-blind treatment phase, early withdrawal (EW) and post-treatment assessments should be obtained. Follow-up visit will take place 7 to 28 days after last dose intake or early withdrawal.
- c. Prestudy therapy will include all medications taken within the 30 days before screening.
- d. Triplicate ECG at Day 1
- e. Supine blood pressure, pulse, and oral temperature. Following the supine vital sign assessment, orthostatic vital signs (blood pressure, pulse) will be taken after standing for at least 3 minutes.
- f. Body weight will be measured with subjects lightly clothed.
- g. Serum chemistry, hematology, coagulation and urinalysis.
- h. Only in case of any clinical significant abnormalities observed at Week 12.
- i ECG should be performed prior to study drug administration, and if possible, at approximately the same time of the day as the screening ECG.
- j Refer to study exclusion criteria for circumstances in which a repeat test during Screening is permitted.
- k Performed for all women. Serum and urine pregnancy test performed at Screening and Follow-up. At all other time points, if the urine pregnancy test is positive, a serum β-hcg test will be performed. Investigators may perform additional pregnancy testing at their discretion as clinically needed.
-  The HAM-A6 is a subscale derived from the SIGH-A (structured interview guide version of the HAM-A).
- m. At each time point, a venous blood sample will be collected for PK analysis of JNJ-42165279 concentration at predose (i.e., prior to morning dose on Days 14 and 28) and 2 hours postdose (only at Day 14).
- n. A 10 mL blood sample will be collected for the pharmacogenomics component of this study. A sample collected at a later time point does not constitute a protocol violation and would not require protocol amendment.
- o. A venous blood sample will be collected for the FAAs (AEA, PEA and OEA) and exploratory biomarkers. The Visit 2 sample must be taken before the first dose of JNJ-42165279 /placebo.
- p. Baseline version completed at Screening.
- q. HDRS17 anxiety/somatization factor score determined from the assessment.

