JNJ-42165279  $C_{max}$  was reached at 0.5 to 2.5 hours postdose (median  $t_{max}$  value, 0.75 hours) following single-dose and once-daily administration of 100 mg. Based on the trough (i.e., predose) concentrations, steady-state conditions were achieved by the third 100-mg daily dose of JNJ-42165279. On average, the  $C_{max}$  and AUC $\tau$  values were 1.13-times and 1.44-times higher on Day 6 relative to Day 1. The similarity between the mean AUC $\infty$  following the 100-mg dose during Part 1 (8,419 ng.h/mL) and the mean AUC $\tau$  on Day 6 during Part 2 (8,644 ng.h/mL) further suggests that the pharmacokinetics of JNJ-42165279 is consistent after single-dose and once-daily repeated administration.

At a dose level of 30 mg or higher, FAAH activity in white blood cells (WBCs) showed a significant decrease with duration of at least 24 hours. At the same time the FAA plasma levels showed a significant increase.

JNJ-42165279 was found to be well tolerated. There were no clinically significant changes in any safety measurements, including clinical laboratories, electrocardiograms (ECGs), vital signs, and physical and neurological examinations. There were no changes or abnormal findings in blood coagulation parameters. There were no deaths, serious adverse events, or discontinuations due to adverse events. All adverse events reported were mild in severity and had resolved by the time of the follow-up visit. The most frequently reported adverse events for subjects receiving JNJ-42165279 were headache, nasal congestion, and dizziness.

In the second multiple ascending dose (MAD) study 42165279EDI1002, four cohorts were studied: healthy males at 25 mg and 75 mg; healthy females (non-child bearing potential) at 100 mg, and healthy elders at 100 mg. Six subjects were on active and two on placebo in each cohort. All subjects were dosed during 10 days. Concentrations of JNJ-42165279 in plasma, urine, and cerebrospinal fluid (CSF) were measured; and FAAH activity in leucocytes (WBCs), and anandamide (AEA), N-oleoylethanolamide (OEA), N-palmitoylethanolamide (PEA) in plasma, and AEA, OEA, and arachidonic acid (AA) in CSF were assayed. Tolerability, including effects on cognition and subjective ratings, were assessed. As dose related increases in coagulation parameters had been observed in male rats, blood coagulation parameters were also included.

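### SAP 8.4 counts orthostatic hypotension by arm only when pulse also rises by more than 15 bpm, so a postural pressure fall without that rise appears in no by-arm orthostatic count

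*SAP*

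**What the plan says.** SAP 8.4 works from within-visit differences: "The orthostatic hypotension measurements will be calculated as the standing measurement minus the supine measurement". The text then gives the definition: "Orthostatic hypotension is defined as a decrease in systolic (>20 mmHg), or diastolic (>10 mmHg) blood pressure after standing for at least 2 minutes", continuing "with an increase in pulse rate of >15 beats per minute". Table 8 repeats the rule with numbered conditions, (1) pulse difference above 15 bpm, (2a) systolic difference below -20 mmHg and (2b) diastolic difference below -10 mmHg, and adds: "Orthostatic hypotension requires that conditions (1) and [(2a) or (2b)] are met".

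The planned by-arm output is a frequency table of orthostatic hypotension at each scheduled time point, at endpoint and at any time in the double-blind phase. No count of subjects meeting (2a) or (2b) alone is specified. The sentence on the listing names a different condition: "Listings will be provided for subjects who have orthostatic hypertension". The SAP does not define that term.

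On timing, the SAP definition refers to at least 2 minutes of standing. Footnote e of the protocol's Time and Events Schedule says "orthostatic vital signs (blood pressure, pulse) will be taken after standing for at least 3 minutes".

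**The concern.** Supine and standing pressure and pulse are collected at screening, Day 1, Weeks 1, 2, 4, 8 and 12, and follow-up. Safety and tolerability is a secondary objective. Dizziness was among the most frequent adverse events on drug in the first Phase 1 study ("The most frequently reported adverse events for subjects receiving JNJ-42165279 were headache, nasal congestion, and dizziness") and among the most common treatment-emergent events in the second (Protocol 1.1).

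A reader of the safety report will take the orthostatic table as the by-arm rate of postural pressure falls. It is the rate of the subset that also had a pulse rise above 15 bpm. A subject with a large fall and a smaller pulse response is not in it. The two arms could differ in postural falls and the table need not show it.

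**Working it through.** The documents give no expected orthostatic rate, so there is no plan figure to reproduce. The check has three parts.

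**1. The rule, coded as written.** Differences are standing minus supine.

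- SAP rule: dPulse > 15 and (dSBP < -20 or dDBP < -10)
- Pressure part alone: dSBP < -20 or dDBP < -10

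| dPulse, dSBP, dDBP | SAP rule | Pressure part |
|---|---|---|
| 16, -21, 0 | counted | counted |
| 16, 0, -11 | counted | counted |
| 15, -21, 0 | not counted | counted |
| 10, -20, -11 | not counted | counted |
| 5, -40, -25 | not counted | counted |
| 0, -60, -30 | not counted | counted |
| 16, -20, -10 | not counted | not counted |
| 20, -5, -5 | not counted | not counted |

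The SAP rule is the pressure part with one further condition, so its count can only be equal or lower.

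**2. Whether Tables 6 and 7 catch the missed subject.** Take supine 135/85 with pulse 70 and standing 95/60 with pulse 75. The differences are 95 - 135 = -40, 60 - 85 = -25 and 75 - 70 = 5, so (2a) and (2b) are met and (1) is not.

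- Table 6 normal ranges are SBP 90-140, DBP 50-90 and pulse 45-90. Every supine and standing value lies inside them.
- Table 7 compares a value with its own baseline, not standing with supine. Its low limits need SBP below 90 or DBP below 50, and 95 and 60 meet neither. The supine values and both pulses are also below its high limits (140, 90 and 90).

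The fall is therefore flagged in no by-arm abnormality table. It remains in the general vital-signs listing, and it contributes to the separate supine and standing summaries.

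**3. Size, on assumptions that are not in the documents.** Let the standing pulse change be normal with mean 8 to 12 bpm and SD 7 to 10. If it is independent of the pressure change, the share of pressure-defined cases left out is P(pulse rise <= 15) = Phi((15 - mean)/SD):

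| SD | mean 8 | mean 10 | mean 12 |
|---|---|---|---|
| 7 | 0.84 | 0.76 | 0.67 |
| 10 | 0.76 | 0.69 | 0.62 |

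Now let pressure fall and pulse rise be correlated. Simulating the systolic criterion only, with SBP change of mean -3 and SD 10, the share left out is:

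| Correlation | pulse mean 10, SD 8 | pulse mean 12, SD 10 |
|---|---|---|
| 0 | 0.73 | 0.62 |
| 0.25 | 0.54 | 0.41 |
| 0.5 | 0.31 | 0.20 |
| 0.7 | 0.13 | 0.06 |
| 0.8 | 0.05 | 0.02 |

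The span over these assumptions is about 2% to 84%. The diastolic criterion is not modelled.

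**The case against.** The strongest reply is that the pulse condition is a deliberate definition. The SAP states it twice and consistently, the protocol has no competing definition, and the documents cite no external standard against which to call it wrong. That stands: replacing the definition would be a preference.

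A reader might infer that the SAP treats a 40 mmHg fall as normal. It does not. Table 8 gives each difference its own limit, so that fall is outside the limit in (2a); it is only not labelled orthostatic hypotension.

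A reader might also infer that a drug lowering both pressure and pulse response would pass as safe. The documents do not support that. Protocol 11.4 plans descriptive statistics for supine and standing pressure and pulse. SAP 8.4 adds summary tables, plots, Tables 6 and 7 and a data listing. SAP 8.2 tabulates treatment-emergent events, including any dizziness, by arm. A shift in mean standing pressure would be visible. What these outputs lack is a by-arm count of subjects with a postural fall.

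The Phase 1 link is suggestive only. Protocol 1.1 also reports no clinically significant vital-sign changes in either study. Orthostatic events are not among the safety events of interest in Protocol 12.2, and nothing in the documents points to a blunted pulse response.

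The objection that the size is assumed also stands. High shares need weak correlation, and a pulse that compensates for the fall implies correlation.

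The two wording points are small. Hypertension is evidently a slip, since the definition, Table 8 and the frequency table all concern hypotension. A reading taken after at least 3 minutes also satisfies at least 2, so no analysed value changes.

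**Conclusion.** The point holds as a gap in tabulation. Following SAP 8.4 exactly, a postural pressure fall with a pulse rise of 15 bpm or less enters no by-arm orthostatic count, and it can pass Tables 6 and 7 as well. The direction is certain: the composite cannot exceed the pressure-only count in either arm. The size is not derivable from the documents. The 2% to 84% range rests wholly on the assumed pulse means, SDs and correlations, and shows only that the gap could be negligible or large.

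The documents do not show that the definition is wrong, that any drug effect would be concealed, or that the arms would be affected differently. No efficacy inference is involved. This is a cheap improvement to a descriptive safety table.

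**What to change.** In SAP 8.4:

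- Keep the composite as defined. Add a by-arm row, at each scheduled time point, at endpoint and at any time in the double-blind phase, for subjects meeting (2a) or (2b) regardless of pulse.
- List these subjects with an indicator for condition (1). Correcting the listing term alone would not be enough, because the listing would then carry the composite and omit the same subjects.
- Change hypertension to hypotension in the listing sentence.
- Reconcile the standing time between SAP 8.4 (at least 2 minutes) and protocol schedule footnote e (at least 3 minutes).

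The thresholds are already in Table 8 and the data are already collected. The cost is SAP wording, one table row and a listing flag. The downside is that the added row will show an incidence at least as high as the composite in both arms, including isolated pressure falls of uncertain clinical meaning. The composite beside it lets the reader see how many also had the pulse rise.

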8.5. Electrocardiogram

A triplicate 12-lead ECG will be obtained at Day 1, otherwise a single, 12-lead ECG will be obtained at each scheduled time point. The ECG variables that will be analyzed are heart rate (HR), ECG intervals (RR, PR, QRS, and QT) as well as corrected QT intervals according to Bazett's formula (QTcB) and Fridericia's formula (QTcF).

The corrected QTcF and QTcB intervals will be calculated according to the following formula:

- *Fridericia*: $QTcF \text{ (msec)} = QT \text{ (msec)} * (HR \text{ (bpm)} / 60)^{1/3}$
- *Bazett*: $QTcB \text{ (msec)} = QT \text{ (msec)} * (HR \text{ (bpm)} / 60)^{1/2}$

Summary tables for actual values and changes from baseline will be presented by treatment group at each scheduled time point and at endpoint. Mean of triplicate ECG values obtained on Day 1 (pre-dose) will be used as a baseline value. Mean-SE plots over time will be presented for ECG values by treatment group. Scatter plots of post-baseline versus baseline values will be presented by treatment group.

The frequency of subjects who are flagged with abnormal values will be summarized by treatment group. The values will be listed for all the subjects with abnormal flags if the ECG values are out of normal range. The following abnormality ranges will be used for ECG parameters (Table 9):

Table 9: ECG Abnormality Ranges

	Low	Normal	High
HR (bpm)	<45	45-90	> 90
PR Interval (msec)	<120	120-220	>220

QRS Interval (msec)	-	<120	≥120
QT Interval (msec)	-	<500	≥500

Criteria for abnormal corrected QTc interval values and changes from baseline are presented in Table 10. Abnormal values and changes will be summarized using frequency distribution tables over time by treatment group. A listing of subjects meeting any of the criteria will be provided.

Table 10: Criteria for Abnormal QTc Values and Changes From Baseline

Parameter	Classification	Criteria
QTc value	Normal	≤450
	> 450 – 480	>450 - ≤480
	> 480 – 500	>480 – ≤500
	> 500	> 500
QTc change from baseline	No concern	≤30
	Concern	>30 – 60
	Clear concern	> 60

These criteria are based on ICH E14 Guideline

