#### Amendment INT-2 (28 Sep 2016)

This amendment is considered to be substantial based on the criteria set forth in Article 10(a) of Directive 2001/20/EC of the European Parliament and the Council of the European Union.

**The overall reason for the amendment:** The overall reason for the amendment is to add neurological examinations to confirm the safety of participation in the trial and treatment with JNJ-42165279.

Applicable Section(s)	Description of Change(s)
Synopsis	Safety Evaluations Physical examination, neurological examination , vital signs, body temperaturewill be performed during the study to monitor subject safety.
Time & Events schedule.	
 
Neurological examination added at screening, during the treatment phase and at the end of treatment visit (or early withdrawal visit)
 
Footnote "t" added : A neurological examination will also be completed in case of adverse event of interest.
 

4.2 Exclusion criteria	Exclusion criteria 6 has been updated as follows: Subject has clinically significant abnormal findings on physical examination, neurological examination or clinically significant abnormal vital signs indicative of untreated illness (such as infection or hypertension).
9.1.2 Screening Phase	Neurological examination added
9.1.3 Double-Blind Treatment Phase	Neurological examination added at Week 4, Week 8 and Week 12 visits
9.2.5 Physical and Neurological Examinations	Title updated and text added: The neurological examination can be adapted as necessary but should include mental status (orientation and memory); oculomotor motion and vision for cranial nerve testing; limb strength and abnormal movements for motor function; and tests of cerebellar function: gait, finger-to-nose, heel-to-shin, and rapid alternating movements. Tests of sensation (e.g., pain, vibration) should be included only if indicated by clinical history/symptoms.
	The neurological examination will be done at screening, during the treatment phase and at the end of treatment visit (or early withdrawal visit) for all subjects. In addition neurological examinations will be completed when event driven. These events of interest include diplopia, vision impairment, gait disturbance and severe headache.
11.4 Safety Analysis	Sub title updated as follows: Physical and Neurological Examinations

Applicable Section(s)	Description of Change(s)
ripplicable beetlon(b)	Description of Change(5)

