# 12-Lead ECG

Heart rate and ECG intervals (RR, PR, QRS and QT) as well as corrected QT intervals according to Bazett's formula (QTcB) and Fridericia's formula (QTcF) from the 12-lead ECG will be summarized at baseline and at each scheduled time point and for changes from baseline using descriptive statistics.

The number and percentage of subjects with at least one occurrence of a treatment-emergent potentially clinically important QTc measurement (QTc value >450, >480, or >500 msec) or with a change from baseline in QTc>30 msec will be summarized by treatment group. Summaries will be provided for all subjects receiving at least one dose of study drug in this study.

Data listings of subjects with any potentially clinically important values (QTc value >450, >480, or >500 msec) or with a change from baseline in QTc >30 msec will be provided.

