# Physical and Neurological Examinations

The number and percentage of subjects with a change from normal at baseline to abnormal at any post-baseline exam will be tabulated by treatment group.

Subjects with abnormal findings will be presented in a data listing.

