2.4. Visit Windows

As subjects do not always adhere to the protocol visit schedule, the following rules are applied to assign actual visits to protocol visits. Listed in [Table 2](#) are the visit windows and the target days for each visit. The reference day is Study Day 1 (which is the first day the study drug was taken in the double-blind phase).

If a subject has 2 or more actual visits in one visit window, the visit closest to the target day will be used as the protocol visit for that visit window. The other additional visit(s) will not be used in the summaries or analyses. If 2 actual visits are equidistant from the target day within a visit window, the later visit is used. If a visit window has no scheduled visits but does have unscheduled visits, then the unscheduled visit closest to the scheduled visit will be used.

All assignments will be made in chronological order. Once a visit is assigned to a visit window, it will no longer be used for a later time point except for the end point. Listed below ([Table 2](#)) are the visit windows and the target days (if applicable) for each visit defined in the protocol.

Table 2: Visit Windows

Parameter	Scheduled Visit Number	Time Interval (label on output)	Time Interval (Day) ¹	Target Time Point (Day)	Analysis Phase ⁵	
MINI Interview, Height, Serology	1	Screening	<1	-28 to -1	Screening	
LSAS, HDRS ₁₇	1	Screening	<1	-28 to -1	Screening	
	2	Baseline	≤1	1	DB Treatment	
	3	Week 1	2 to 10	7	DB Treatment	
	4	Week 2	11 to 21	14	DB Treatment	
	5	Week 4	22 to 42	28	DB Treatment	
	7	Week 8	43 to 70	56	DB Treatment	
SIGH-A	2	Baseline	≤1	1	DB Treatment	
	3	Week 1	2 to 10	7	DB Treatment	
	4	Week 2	11 to 21	14	DB Treatment	
	5	Week 4	22 to 42	28	DB Treatment	
	7	Week 8	43 to 70	56	DB Treatment	
	9	Week 12 End Point ²	71 to End of DB ⁴	84	DB Treatment	
CGI - I	3	Week 1	2 to 10	7	DB Treatment	
	4	Week 2	11 to 21	14	DB Treatment	
	5	Week 4	22 to 42	28	DB Treatment	
	7	Week 8	43 to 70	56	DB Treatment	
	9	Week 12 End Point ²	71 to End of DB ⁴	84	DB Treatment	
	SDS, GAD-7, SHAPS, MOS Sleep – R, Q-LES-Q	2	Baseline	≤1	1	DB Treatment
5		Week 4	2 to 42	28	DB Treatment	
7		Week 8	43 to 70	56	DB Treatment	
9		Week 12 End Point ²	71 to End of DB ⁴	84	DB Treatment	
Self-assessment of treatment experience	9	Week 12 End Point ²	2 to End of DB ⁴	84	DB Treatment	
12-Lead ECG, Body Weight	1	Screening	<1	-28 to -1	Screening	
	2	Baseline	≤1	1	DB Treatment	
	5	Week 4	2 to 56	28	DB Treatment	

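### The SAP does not carry over two by-arm any-occurrence safety tables that protocol 11.4 specifies (physical/neurological examination and QTc), and the visit rule in SAP 2.4 conflicts with the any-time counts promised in 8.3 and 8.4

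*SAP*

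**What the plan says.** **Examinations.** Protocol 11.4, under Physical and Neurological Examinations, says that the number and percentage of "subjects with a change from normal at baseline to abnormal at any post-baseline exam will be tabulated by treatment group", with a listing of abnormal findings in addition. SAP 8.4 ends with one sentence on the subject: "Physical examination abnormalities and neurological examination results will be listed".

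**QTc.** Protocol 11.4, under 12-Lead ECG, specifies: "The number and percentage of subjects with at least one occurrence of a treatment-emergent potentially clinically important QTc measurement" (thresholds 450, 480 and 500 msec), or with a change from baseline above 30 msec, by treatment group. SAP 8.5 sets QTc categories in Table 10 and says: "Abnormal values and changes will be summarized using frequency distribution tables over time by treatment group". A listing of subjects meeting a criterion follows.

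**Any-time counts.** SAP 8.3 (markedly abnormal laboratory values) and 8.4 (treatment-emergent vital-sign abnormalities and orthostatic hypotension) promise incidence by visit, at endpoint and at any time in the double-blind phase. SAP 2.4 keeps one visit per window, the one closest to the target day. Of the rest it says: "The other additional visit(s) will not be used in the summaries or analyses". Its provision for unscheduled visits opens with the condition "If a visit window has no scheduled visits but does have unscheduled visits", which implies that they do not otherwise count.

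**The concern.** Safety and tolerability is a secondary objective. SAP section 1 records that the study was suspended in January 2016, unblinded and given an interim safety analysis. Amendment INT-2 followed, and its stated purpose was "to add neurological examinations to confirm the safety of participation in the trial". The by-arm count of subjects who became abnormal is the comparative result those examinations were meant to yield. A listing leaves the reader to build it by hand, and a table built after unblinding is not pre-specified.

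A by-visit QTc table is not a substitute for an any-occurrence count, because one subject can appear at both visits.

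The laboratory and vital-sign any-time tables are promised but can be programmed in two ways. The two ways differ exactly where an abnormal result has been rechecked.

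**Working it through.** The plan gives no figure to reproduce here. The check is a comparison of texts, with one short calculation and one illustration.

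**1. Does another SAP output supply the two tables?**

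| Output in protocol 11.4 | SAP output | By-arm any-occurrence count? |
|---|---|---|
| Normal to abnormal at any later physical or neurological examination | Listing (8.4) | No |
| At least one QTc above 450, 480 or 500 msec, or change above 30 msec | Table 10 categories over time, plus listing (8.5) | Not stated |

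The over-time wording cannot be assumed to include an any-time row, because the SAP separates the two itself. In 8.4, Table 6 abnormalities are tabulated over time, while Table 7 abnormalities and orthostatic hypotension are tabulated at each time point and also at any time. Section 8.3 names the any-time count for laboratory values as well. Section 8.5 does not.

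**2. How far do by-visit QTc counts fix the any-occurrence count?**

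Inputs:
- Scheduled on-treatment ECGs after Day 1: Week 4 and Week 12, so two (Time and Events Schedule).
- Subjects per arm: 137 / 2 = 68.5, about 68 (protocol 11.2, 1:1 allocation).
- Subjects above a threshold at each visit: a = b = 3. This is an assumption; the documents give no value.

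With visit counts a and b, the number with at least one occurrence lies between max(a, b), when the same subjects are flagged twice, and a + b, when no subject is.

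- Lower bound: max(3, 3) = 3; 3/68 = 4.4%.
- Upper bound: 3 + 3 = 6; 6/68 = 8.8%.

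The same by-visit table is therefore compatible with a twofold range. The bounds apply to the two scheduled ECGs only. Once unscheduled ECGs count, a + b is no longer an upper limit.

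For examinations there is no by-arm figure to bound. The schedule has three on-treatment neurological examinations (Weeks 4, 8 and 12) plus event-driven ones, and two post-baseline physical examinations (Week 12 and follow-up).

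**3. What does the SAP 2.4 rule do to an any-time count?**

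Take the laboratory Week 4 window in SAP Table 2 (Days 22 to 35, target Day 28) and the Table 5 criterion for ALT, above 3 x ULN. The values below are assumed.

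| Results in the window | Visit kept under 2.4 | Counted if only kept visits are used | Counted if all double-blind values are used |
|---|---|---|---|
| Day 26: 3.4 x ULN; Day 29 repeat: 2.6 x ULN | Day 29 | No | Yes |
| Scheduled Day 28: 2.4 x ULN; unscheduled Day 33: 3.6 x ULN | Day 28 | No | Yes |

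Such repeats are to be expected: protocol 3.3.1 asks for liver-test elevations to be confirmed by repeat, and 9.1.1 allows additional measurements after abnormal safety findings. How many subjects would be affected, and in which arm, cannot be computed from the documents.

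**The case against.** **SAP 8.5 has a subject-level sentence.** It promises, by arm, the frequency of subjects flagged with abnormal values, without tying this to visits, and QTcB and QTcF are among the variables the section analyses. But the sentence leads into Table 9, which covers heart rate, PR, QRS and QT and has no QTc row; QTc follows separately under Table 10. It does not clearly supply the protocol's count.

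**The information is not lost.** The QTc listing identifies the subjects concerned, and the examination results are listed. Protocol 9.2 requires clinically relevant changes to be recorded as adverse events, and SAP 8.2 tabulates treatment-emergent events by arm. This stands. It limits the gap mainly to findings not judged clinically relevant and to the lack of pre-specified tables.

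**Treatment-emergent QTc hardly needs defining.** Exclusion criterion 7 names QTc above 450 msec at screening or baseline as an excluding finding, so most later values above 450 are new in any case. This also stands, and a short qualifier is enough.

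**SAP 2.4 concerns by-visit presentation.** Its stated purpose is to assign actual visits to protocol visits. Section 2.3.5 places all data from baseline to the end point or early-withdrawal visit in the double-blind phase, and 8.3 defines markedly abnormal on post-baseline values without mentioning windows. These favour using all the data. A reader might infer that abnormal repeat values will be discarded; the documents do not establish that. The literal exclusion is nonetheless written without a safety exception.

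**Further inferences the documents do not support.** A reader might take the absence of a neurological row in SAP Table 2 as an omission, but the table as available has visibly lost rows (LSAS has no Week 12 row either). A reader might say that repeated ECG readings are left unhandled, but 8.5 specifies a single ECG after Day 1 and for the Day 1 triplicate states: "Mean of triplicate ECG values obtained on Day 1 (pre-dose) will be used as a baseline value". Analysing incorrectly treated subjects as randomized (SAP 2.1) contradicts no protocol text and has no effect unless mis-dosing occurs.

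**Conclusion.** The mismatch is real and specific. For examinations the SAP replaces a by-arm tabulation with a listing. For QTc it replaces an any-occurrence count with by-visit tables and a listing, and its own wording elsewhere shows that an any-time count is named where one is intended. SAP 2.4 adds a textual conflict with the any-time counts in 8.3 and 8.4; the all-data reading is the better supported one but should be stated.

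The size is modest. The 4.4% to 8.8% range rests on the assumed 3 subjects per visit, about 68 per arm and scheduled ECGs only. It shows that the count is undetermined and is not an estimate for this trial. The size and direction of any undercount under SAP 2.4 are unknown. A reader might conclude that the safety evaluation is compromised; the documents do not support that, since the data are collected, listed and partly summarized as adverse events, and the primary efficacy analysis is unaffected. The tables should still be specified in the SAP, or the departure from protocol 11.4 stated and justified.

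**What to change.** - **SAP 8.4:** add a by-arm table of subjects normal at baseline and abnormal at any later physical examination, and the same for any later neurological examination, scheduled or event-driven. State the denominator as subjects with a normal baseline examination and at least one later one; subjects treated before the January 2016 suspension predate the amendment that added the neurological examination.
- **SAP 8.5:** add a by-arm count and percentage of subjects with one or more post-baseline double-blind values above 450, 480 or 500 msec who were not in that category at baseline, or with an increase above 30 msec, separately for QTcB and QTcF.
- **SAP 2.4:** state that any-time incidence counts use all post-baseline double-blind values, scheduled and unscheduled, while by-visit tables keep the window rule.

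The cost is two tables and a few sentences, with no new data. The downside is that any-time counts rise with the frequency of retesting, so the number of unscheduled assessments should be reported by arm beside them.
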